**Up-titration period (4 weeks):**

- Days 1-4 (0.25 mg/day): 1 tablet in the morning, none in the evening
- Days 5-8 (0.5 mg/day): 1 tablet in the morning and 1 tablet in the evening
- Days 9-12 (0.75 mg/day): 2 tablets in the morning, 1 tablet in the evening
- Days 13-16 (1.0 mg/day): 2 tablets in the morning, 2 tablets in the evening
- Days 17-20 (1.25 mg/day): 3 tablets in the morning, 2 tablets in the evening
- Days 21-24 (1.5 mg/day): 3 tablets in the morning, 3 tablets in the evening
- Days 25-28 (1.75 mg/day): 4 tablets in the morning, 3 tablets in the evening

**Constant dose period (2 weeks):**

- Days 29-42 (2 mg/day): 4 tablets in the morning, 4 tablets in the evening

**Down-titration period (2 weeks, down-titration by 0.25 mg/day every 2 days):**

- Days 43-44 (start of down-titration period [1.75 mg/day])
- Days 45-46 (1.5 mg/day)
- Days 47-48 (1.25 mg/day)
- Days 49-50 (1 mg/day)
- Days 51-52 (0.75 mg/day)
- Days 53-54 (0.5 mg/day)
- Days 55-56 (0.25 mg/day)

Patients in the placebo arm will follow the same dose escalation, constant dose and down-titration schedule, but will be taking the matching placebo tablets. Patients who have intolerable AEs during the 28-day up-titration period will be allowed to return to the previous tolerated dose at the discretion of the Investigator, or they may withdraw from the study if they so choose.

Each patient is expected to participate in the study for approximately 10 weeks, not including screening. Patients will be treated with IMP for a total of 8 weeks (56 days).

The timing of events is summarized in Table 8.1-1. Study assessments are described in Section 11.

Table 8.1-1 Schedule of events

Study visit number		Visit 1	Visit 2	Visit 3	Visit 4	Visit 5	Visit 6	Visit 7	Visit 8	Visit 9
Study period		Screening	Baseline	Phone Safety Visit	Clinic Safety Visit	Clinic Safety Visit	Clinic Efficacy Visit	Clinic Efficacy Visits	Phone Safety Visit	Follow-up Clinic Visit 
Study day	Protocol Section	Day -28 to Day -5	Day 1	Day 7 ±1 day	Day 14 ±2 days	Day 21 ±2 days	Day 28 ±2 days	Day 42 ±2 days	Day 49 ±2 days	Day 70 ±7 days
Informed Consent	14.3	X								
Eligibility criteria	9.4 & 9.5	X	X 							
Demographics	11.1.3	X								
Vital signs 	11.2.3	X	X		X	X	X	X		X
Physical examination	11.2.2	X								X
Body weight and height 	11.1.4	X								X
Hoehn and Yahr scale 	11.1.8	X	X							
Medical and psychiatric history	11.1.5	X								
Pregnancy test 	11.1.7	X	X							X
12-lead ECG	11.2.4	X	X		X	X	X	X		X
Safety laboratory 	11.2.6	X	X		X	X	X	X		X
MMSE	11.1.9	X								
C-SSRS 	11.2.5	X	X		X	X	X	X		X
UPDRS 	11.3.1	X	X				X	X		X
Diary and wearable device training	11.3.3&11.3.6	X	X							
Randomization	9.9		X							
Study drug dispensing	10.5		X				X	X		
Treatment (Day 1 - Day 56)	10.6					X				

Study visit number		Visit 1	Visit 2	Visit 3	Visit 4	Visit 5	Visit 6	Visit 7	Visit 8	Visit 9
Study period		Screening	Baseline	Phone Safety Visit	Clinic Safety Visit	Clinic Safety Visit	Clinic Efficacy Visit	Clinic Efficacy Visits	Phone Safety Visit	Follow-up Clinic Visit 
Study day	Protocol Section	Day -28 to Day -5	Day 1	Day 7 ±1 day	Day 14 ±2 days	Day 21 ±2 days	Day 28 ±2 days	Day 42 ±2 days	Day 49 ±2 days	Day 70 ±7 days
Diary data collection 	11.3.3		X				X	X		
Wearable device data collection 	11.3.6		X				X	X		
L-DOPA challenge	11.3.1		X				X	X		
UDysRS	11.3.2		X				X	X		
Video taping (UDysRS)	11.3.2		X				X	X		
CGI-S/CGI-C 	11.3.5		X				X	X		
KPPS	11.4.1		X				X	X		
PDQ39	11.4.2		X				X	X		
HADS	11.4.3		X				X	X		
ICIQ-OAB	11.4.4		X				X	X		
ESS	11.4.5		X				X	X		
NLX-112 plasma concentration sampling	11.4.6				X	X	X	X		X
Drug accountability	10.5						X	X		X
Baseline symptoms	11.1.10	X								
Adverse events 	11.2.1						X			
Prior and concomitant medications	11.1.6						X			

CGI-S/CGI-C=Clinical Global Impression of Severity and Clinical Global Impression of Change, C-SSRS=Columbia Suicide Severity Rating Scale, ESS=the Epworth Sleepiness Scale, HADS=the Hospital Anxiety Depression Scale, ICIQ-OAB=the International Consultation on Incontinence Questionnaire Overactive Bladder Module,

KPPS=the King's Parkinson's disease Pain Scale, UPDRS=the Unified Parkinson's Disease Rating Scale, MMSE=Mini Mental Status Exam, PDQ39=the Parkinson's disease Quality of Life Scale (39-item), UDysRS=the Unified Dyskinesia Rating Scale

1. Also early withdrawal follow-up visit
2. Confirmation of eligibility
3. Blood pressure (including orthostatic hypotension assessment), pulse, respiratory rate and temperature. At screening and baseline (Visit 1 and Visit 2), vital signs to assess orthostatic hypotension will be conducted in triplicate, 15-20 minutes apart, with the average of the 3 assessments used for exclusion.
4. Body weight at Visit 1 and Visit 9. Height at Visit 1 only.
5. The Modified Hoehn and Yahr scale will be used to establish the PD stage of the patient.
6. Women of child-bearing potential only.
7. Hematology, coagulation, serum biochemistry and urinalysis.
8. C-SSRS: the baseline scale will be used at the first assessment (screening, Visit 1) and the follow-up scale will be used at all subsequent visits.
9. UPDRS - Screening: part IV only. Other visits: parts I-IV
10. PD Home Dyskinesia Diary: 2 consecutive 24-hour diaries taken prior to the visits indicated above.
11. Wearable data collection will take place during a 2-day period prior to the visits indicated above.
12. CGI-S at baseline (Day 1, Visit 2), CGI-C at other visits.
13. Collection of AEs from the first dose of IMP.

## 8.2 Order of assessments

Safety assessments should be performed before the L-DOPA challenge at Visit 2, 6 and 7.

The efficacy assessments at Visits 2, 6 and 7 should be performed in the order outlined in Table 8.2-1.

**Table 8.2-1 Order of efficacy assessments**

Assessment	Assessor	
	Investigator	Patient
UDysRS (Parts III and IV repeated 3 times at approximately 30, 60 and 90 minutes after the 150% L-DOPA challenge)	X	
UPDRS part III in ON (within 30-90 minutes after the 150% L-dopa challenge)	X	
UPDRS parts I, II and IV	X	X 
CGI-C	X	
KPPS	X	
UDysRS (Parts I and II)		X
PDQ39		X
HADS		X
ESS		X
ICIQ-OAB		X

CGI-C=Clinical Global Impression of Change, ESS=the Epworth Sleepiness Scale, HADS=the Hospital Anxiety Depression Scale, ICIQ-OAB=the International Consultation on Incontinence Questionnaire Overactive Bladder Module, KPPS=the King's Parkinson's disease Pain Scale, UPDRS=Unified Parkinson's Disease Rating Scale, PDQ39=the Parkinson's disease Quality of Life Scale (39-item), UDysRS=the Unified Dyskinesia Rating Scale

End of Part I and Part II

## 8.3 Rationale for study design

This is a double-blind, randomized, placebo-controlled Phase 2a study evaluating the safety, tolerability, and preliminary efficacy of up to 2 mg/day of NLX-112 versus placebo in PD patients with moderate to severe LID. NLX-112 will be up-titrated to either 2 mg/day (1 mg BID) or to the highest well-tolerated dose less than 2 mg/day over 4 weeks, maintained at the well-tolerated dose for an additional 2 weeks, and then down-titrated over 2 weeks. The study will provide important safety and preliminary efficacy data to support the design of further studies in PD-LID patients.

Since NLX-112 is being developed as an anti-dyskinetic therapy, its anti-dyskinetic capacity will be addressed in the present study. Since dyskinésias vary over time, the patients will be given 150% of their regular L-DOPA dose as a challenge before the UDysRS assessment(s). The maximum L-DOPA dose to be administered in the study is 250 mg. 150% of the regular L-DOPA dose as a challenge is routinely given when L-DOPA tests are done to evaluate L-DOPA responsivity in standard clinical practice. Should the Investigator consider it

medically warranted to reduce the L-DOPA challenge in a specific patient for safety or tolerability reasons, this should be approved by the Sponsor prior to implementation. It is critical that the same dose is given at all visits with L-DOPA challenges for a given patient.

A placebo control will be used to establish the frequency and magnitude of changes in endpoints that may occur in the absence of active treatment.

Randomization will be used to minimize bias in the assignment of patients to dose groups and to increase the likelihood that known and unknown subject attributes (e.g., demographic and baseline characteristics) are evenly balanced across treatment groups.

Blinded treatment will be used to reduce potential bias during data collection and evaluation of endpoints.

Blood samples to be possibly used for measurement of plasma NLX-112 concentration will be collected at clinic visits on Days 14, 21, 28, 42 and 70. These plasma levels could serve as a rough measure of compliance with the study medication regimen and Sponsor may choose to determine the NLX-112 plasma concentration if deemed useful to answer any questions regarding compliance.

#### 8.4 Selection of dose

The effective doses of NLX-112 in PD-LID patients were estimated based on PK and pharmacodynamic data from animal studies (Neurolisis Position paper NSR-16-005-02). The methods employed in these studies have previously been used with a number of CNS compounds and have generally predicted outcomes in an appropriate clinical range. The methods include: allometric scaling between rat and human; comparisons of total and free plasma exposure between rat and human; translational biomarker study on corticosterone / cortisol release; translational biomarker study on body temperature decreases; and physiologically-based pharmacokinetic and pharmacodynamic (PKPD) modelling.

Dosing calculations based on biomarker data carry considerable face validity because cortisol release and hypothermia are well-characterized responses to central 5-HT1A receptor agonists and are highly translatable between rodent and human: they predicted doses in the range 0.3 to 1.25 mg. These dose predictions tally with those derived from plasma exposure calculations (0.5 to 1.25 mg) and allometric scaling predictions (0.45 mg). Overall, the results of these analyses suggest that doses in the range from 0.3 to 1.25 mg/day may be efficacious in treating PD-LID. The PKPD modeling study yielded a somewhat higher estimate of 3 mg.

It should be noted that repeated dosing of NLX-112 results in an approximate 2-fold accumulation of drug at steady state, and exposure levels of NLX-112 in elderly males were 30% higher than in young male volunteers (as shown in a Phase 1 study in aged volunteers – Study F13640 GE102). This is relevant to the present study because the majority of PD patients are typically over 65 years old.

Taken together, these data suggest that efficacious doses of NLX-112 for treatment of LID will be in the low milligram or sub-milligram range.

## 9 STUDY POPULATION

Prospective approval of protocol deviations to eligibility criteria, also known as protocol waivers or exemptions, is not permitted.

### 9.1 Recruitment

Potential participants in the study will be identified according to the routines of the clinical study sites. Patients will be recruited at 5 clinical sites, with an average of 4 to 6 patients per site.

### 9.2 Screening and enrolment log

Investigators must keep a record of all screened patients even if they were not subsequently included in the study. This information is necessary to verify that patients were selected without bias. The reason for screen failure should be stated for all patients screened but not included. The reason for withdrawal should be stated for all patients included but not completed.

A screening number will be allocated to each patient in connection to the informed consent process at the Screening visit. The screening number is generated automatically in the electronic case report form (eCRF). The screening number will allow identification of patients irrespective of their possible eligibility for the study.

Patients that are included and randomized will be assigned a randomization number.

If a patient cannot receive the planned dose of IMP within 28 days after screening (*i.e.*, the time interval between signing informed consent until dose administration) the patient should be rescreened before proceeding in the study.

### 9.3 Number of patients

A total of 24 patients will be randomized in the study.

To account for potential drop-outs, additional patients may be included in the study. For replacements of patients who discontinue from the study, see Section 9.8.

### 9.4 Inclusion criteria

To be eligible to participate in the study, a patient must meet ALL of the following inclusion criteria:

1. Patient is 30 – 85 years old (inclusive) with a diagnosis of idiopathic PD according to the UK Parkinson's Disease Society Brain Bank Clinical Diagnosis criteria.
2. PD patient is stably and optimally treated with L-DOPA; other anti-PD treatments are allowed if used for at least 4 weeks of previous continuous treatment.
3. Patient agrees to be challenged with 150% of their normal L-DOPA dose (maximum L-DOPA dose 250 mg) 30 minutes prior to efficacy assessments at baseline (Visit 2) and at the 2 efficacy clinic visits (Visits 6 and 7).

4. PD patient exhibits troublesome peak-dose LID, confirmed by a score of at least 1 on part IV, item 33 (disability) of the UPDRS at screening (Visit 1) and at Day 1 (baseline, Visit 2).
5. At least 90 minutes in total for each 24-hour period during 2 days are indicated as “ON with troublesome dyskinesia” (according to the PD Home Dyskinesia Diary) prior to Day 1 (baseline, Visit 2).
6. Patient (and/or caregiver) demonstrates ability to accurately complete the PD Home Dyskinesia Diary entries during the screening visit.
7. Patient can read well enough to understand the informed consent document and other subject materials.
8. Female patients of child-bearing potential must have a negative urine pregnancy test at screening (Visit 1) and on Day 1 (Visit 2), must agree to avoid pregnancy during the study, and must practice abstinence (only allowed when this is the preferred and usual lifestyle of the subject) or must agree to use a highly effective method of contraception with a failure rate of < 1% to prevent pregnancy (combined [oestrogen and progestogen containing] hormonal contraception associated with inhibition of ovulation [oral, intravaginal, transdermal], progestogen-only hormonal contraception associated with inhibition of ovulation [oral, injectable, implantable], intrauterine device [IUD] or intrauterine hormone-releasing system [IUS]) starting from 4 weeks prior to administration of the study drug and continuing during the course of the study until 4 weeks after last after IMP administration. Female subjects must agree to refrain from donating eggs from the date of dosing until 3 months after dosing with the IMP. Their male partner must agree to use a condom during the same time frame if he has not undergone vasectomy.

Females of non-childbearing potential are defined as pre-menopausal females who are sterilised (tubal ligation or permanent bilateral occlusion of fallopian tubes); or females who have undergone hysterectomy or bilateral oophorectomy; or post-menopausal defined as 12 months of amenorrhea (in questionable cases a blood sample with detection of follicle stimulating hormone [FSH] 25-140 IE/L is confirmatory).

Male patients must be either vasectomised, consent to use condom or practice sexual abstinence to prevent pregnancy and drug exposure of a partner and refrain from donating sperm from the date of dosing until 3 months after dosing with the IMP. Their female partner of child-bearing potential must use highly effective contraceptive methods with a failure rate of < 1% to prevent pregnancy (see above) during the same period.

## 9.5 Exclusion criteria

If the patient meets any of the following criteria, the patient MUST NOT be enrolled:

1. Patient has severe PD with a Hoehn and Yahr stage = 5.
2. Patient has unstable medical status, prior brain surgery against tumors or hemorrhage (excluding deep brain stimulation [DBS], i.e., DBS patients will be allowed to be enrolled) or is scheduled to receive surgery during the trial period.

3. Patient has orthostatic hypotension: a decrease in systolic blood pressure (at least 20 mm Hg) or diastolic blood pressure (at least 10 mm Hg) within 3 minutes of the patient standing up, compared to pressures obtained while in a sitting position for at least 5 minutes. At screening and baseline visits (Visit 1 and Visit 2), vital signs to assess orthostatic hypotension will be conducted in triplicate, 15-20 minutes apart, with the average of the 3 assessments used for exclusion.
4. Patient has dementia (MMSE <20).
5. Patient has clinically significant renal or liver disorder.
6. Patient currently exhibits generalized obsessive-compulsive disorder, panic disorder, bipolar disorder, post-traumatic stress syndrome (PTSD), clinically significant parasomnias or any other psychotic disorder as established by structured clinical interview for DSM disorders (SCID). Visual hallucinations are allowed.
7. Any suicidal actions in the past 2 years (per investigator judgement i.e. actual attempt, interrupted attempt, aborted attempt, or preparatory acts or behavior).
8. Any suicidal ideation of type 4 or 5 in the C-SSRS in the past 3 months (i.e. active suicidal thought with intent but without specific plan, or active suicidal thought with plan and intent).
9. Patient has taken an anti-convulsant, an anti-psychotic (except quetiapine), pindolol, tertatolol or buspirone within 4 weeks of baseline (Day 1, Visit 2).
10. Patient has taken any medication, within 4 weeks of baseline (Day 1, Visit 2) that inhibits or up-regulates CYP4503A4, see Section 9.6.2.
11. Patient is concurrently participating in another investigational drug trial or has participated in another investigational drug trial within the past 3 months.
12. Patient is at high risk of non-compliance in the Investigator's opinion.

## 9.6 Restrictions during the study

The patients must be willing to comply to the following restrictions during the entire study duration *i.e.*, from screening to the end-of-study visit.

### 9.6.1 *General restrictions*

- Contraception Requirements:

All females of child-bearing potential must use highly effective contraception (defined in inclusion criterion No 8) or practice abstinence during the study and for 4 weeks after IMP administration and refrain from donating eggs from the date of dosing until 3 months after dosing with the IMP. Their male partner is expected to use a condom during the same time frame if he has not undergone vasectomy.

The male patients must be either vasectomised, consent to use condom or practice sexual abstinence to prevent pregnancy and drug exposure of a partner and refrain from donating sperm from the date of dosing until 3 months after dosing with the IMP. Their fertile female partner is expected to use highly effective contraceptive methods to prevent pregnancy (for details, refer to inclusion criterion No 8) during the same period.

- Meals and Dietary Restrictions: The IMPs should be taken during a meal and swallowed with approximately 240 mL of tap water.
- Products affecting CYP450 3A4 activity: Consumption of grapefruit and/or grapefruit containing products or star fruit is not allowed during the study.
- Blood donation: The patients must not donate blood or plasma during the study until 3 months after the final medical examination at the end-of-study visit.

#### 9.6.2 ***Prior and concomitant therapy***

Use of an anti-convulsant, an anti-psychotic (except quetiapine), pindolol, tertatolol or buspirone within 4 weeks of baseline (Day 1, Visit 2) and during the study is prohibited.

In addition, the following drugs which may affect CYP450 3A4 activity are prohibited from 4 weeks prior to baseline (Day 1, Visit 2) and during the study:

**Inducers:** barbiturates, carbamazepine, efavirenz, glucocorticoids, modafinil, nevirapine, phenobarbital, phenytoin, rifampin, Saint-John's wort, troglitazone, oxcarbazepine, pioglitazone, rifabutin.

**Inhibitors:** amiodarone, aprepitant, chloramphenicol, cimetidine, clarithromycin, delavirdine, diethyl-dithiocarbamate, diltiazem, erythromycin, fluconazole, fluvoxamine, gestodene, imatinib, indinavir, itraconazole, ketoconazole, mifepristone, nefazodone, nelfinavir, norfloxacin, norfluoxetine, mibepradil, verapamil, ritonavir, voriconazole.

Prohibited concomitant medications also include those, which in the Investigator's opinion (with Sponsor agreement), may negatively interact with the study medication NLX-112 and lead to untoward side effects or otherwise affect patient safety.

Medications considered necessary for the patient's safety and wellbeing may be given at the discretion of the Investigator. Following consultation with the Sponsor, the Investigator will determine whether or not the patient should continue in the study.

Use of selective serotonin reuptake inhibitors (SSRIs), benzodiazepines and amantadine is allowed as is occasional use of apomorphine as judged by the Investigator. In addition, Covid-19 vaccination is allowed.

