**Exclusion criteria:**

1. Patient has severe PD with a Hoehn and Yahr stage = 5.
2. Patient has unstable medical status, prior brain surgery against tumors or hemorrhage (excluding deep brain stimulation [DBS], i.e., DBS patients will be allowed to be enrolled) or is scheduled to receive surgery during the trial period.
3. Patient has orthostatic hypotension: a decrease in systolic blood pressure (at least 20 mm Hg) or diastolic blood pressure (at least 10 mm Hg) within 3 minutes of the patient standing up, compared to pressures obtained while in a sitting position for at least 5 minutes. At screening and baseline visits (Visit 1 and Visit 2), vital signs to assess orthostatic hypotension will be conducted in triplicate, 15-20 minutes apart, with the average of the 3 assessments used for exclusion.
4. Patient has dementia (MMSE <20).
5. Patient has clinically significant renal or liver disorder.
6. Patient currently exhibits generalized obsessive-compulsive disorder, panic disorder, bipolar disorder, post-traumatic stress syndrome (PTSD), clinically significant parasomnias or any other psychotic disorder as established by structured clinical interview for DSM disorders (SCID). Visual hallucinations are allowed.

7. Any suicidal actions in the past 2 years (per investigator judgement i.e. actual attempt, interrupted attempt, aborted attempt, or preparatory acts or behavior).
8. Any suicidal ideation of type 4 or 5 in the C-SSRS in the past 3 months (i.e. active suicidal thought with intent but without specific plan, or active suicidal thought with plan and intent).
9. Patient has taken an anti-convulsant, an anti-psychotic (except quetiapine), pindolol, tertatolol or buspirone within 4 weeks of baseline (Day 1, Visit 2).
10. Patient has taken, within 4 weeks of baseline (Day 1, Visit 2), any medication that inhibits or up-regulates CYP450 3A4.
11. Patient is concurrently participating in another investigational drug trial or has participated in another investigational drug trial within the past 3 months.
12. Patient is at high risk of non-compliance in the Investigator's opinion.

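### Section 9.6.2 of the protocol bans fluvoxamine by name during the study, then allows SSRIs as a class with no exception

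*Protocol*

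**What the plan says.** Section 9.6.2 of the protocol sets the medication rules in this order.

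- It prohibits anti-convulsants and "an anti-psychotic (except quetiapine), pindolol, tertatolol or buspirone" before baseline and during the study. This sentence writes out its own exception, for quetiapine.
- It names inducers and inhibitors of CYP3A4 that "are prohibited from 4 weeks prior to baseline (Day 1, Visit 2) and during the study". Part of the inhibitor list reads "erythromycin, fluconazole, fluvoxamine, gestodene, imatinib, indinavir, itraconazole, ketoconazole, mifepristone, nefazodone, nelfinavir, norfloxacin, norfluoxetine".
- It adds to the prohibited drugs any that the Investigator, with the Sponsor's agreement, thinks may interact adversely with NLX-112.
- It lets the Investigator give medication needed for the patient's safety and wellbeing, and then says "Following consultation with the Sponsor, the Investigator will determine whether or not the patient should continue in the study".
- It closes with the permissions: "Use of selective serotonin reuptake inhibitors (SSRIs), benzodiazepines and amantadine is allowed".

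Exclusion criterion 10 in Section 9.5 is "Patient has taken any medication, within 4 weeks of baseline (Day 1, Visit 2) that inhibits or up-regulates CYP4503A4, see Section 9.6.2". The synopsis has the same criterion without the cross-reference. Section 9.8.1 lists taking a prohibited drug among the reasons for discontinuation, on the judgement of the Investigator, the Sponsor or both.

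**The concern.** A site needs one answer to the question of whether a patient on study may be given fluvoxamine. The inhibitor list says no. The SSRI sentence, which comes last and carries no qualification, says yes. The section states no order of precedence, and the quetiapine wording shows that its authors wrote an exception where they intended one.

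The restriction has a purpose. Section 6.1.3 identifies CYP3A4 as the main route by which NLX-112 is metabolised. Section 9.6.1 carries the same restriction into diet: "Consumption of grapefruit and/or grapefruit containing products or star fruit is not allowed during the study". Safety and tolerability is the primary objective, and about 16 patients are to receive active drug. A site that follows the SSRI sentence literally could give a drug that the same section bans because of this enzyme. Another site could treat the same prescription as a protocol violation.

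**Working it through.** No arithmetic is involved beyond a count of the list. The check is to set the rules side by side.

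**Count of the list in Section 9.6.2.** There are 14 inducers and 25 inhibitors, so 14 + 25 = 39 entries. Fluvoxamine is the 11th inhibitor and norfluoxetine the 21st. Fluoxetine is not an entry in either list.

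**What each rule says in each case.**

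| Case | Exclusion 10 | CYP3A4 list | SSRI sentence | Result |
|---|---|---|---|---|
| Fluvoxamine in the 4 weeks before baseline | Excluded | Prohibited | Allowed | Settled: patient not eligible |
| Fluvoxamine started after Day 1 | Does not apply | Prohibited | Allowed | Contradiction |
| SSRI not on the list, started after Day 1 | Does not apply | Silent | Allowed | Allowed |

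The first row is settled because exclusion 10 points to the list, the list names fluvoxamine, and Section 9 permits no waiver of an eligibility criterion. The second row is the only one in which two operative rules collide. Exclusion 10 cannot resolve it, because it looks back from baseline.

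**Whether another clause resolves the second row.**

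- The interaction clause depends on the Investigator's opinion and the Sponsor's agreement. A site that reads SSRIs as allowed has no prompt to seek either.
- The necessary-medication clause decides whether the patient continues in the study. It does not say whether fluvoxamine is permitted.
- The discontinuation criterion in Section 9.8.1 presupposes that the drug is prohibited, which is the point in dispute.

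Each clause makes an unnoticed problem less likely. None amends the SSRI sentence.

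**One point from outside the documents.** The protocol does not state that fluvoxamine is an SSRI; this is general pharmacology. The protocol relies on its readers for such knowledge, because it uses the class name without listing its members.

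**The case against.** The strongest reply is that a ban by name governs over a permission by class, so any careful reader reaches the intended answer. What is left is a new fluvoxamine prescription after Day 1, in a 24-patient study with 8 weeks of dosing, at a site that overlooks a list in the same section. The interaction clause can reach any SSRI, prohibited medication can lead to discontinuation, and Section 11.1.6 requires all medication and all changes in it to be recorded.

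Most of this stands. The named ban is very likely what was meant, and the practical gap is small. It remains true that the section does not say which rule prevails and that the clauses relied on are discretionary. A site should not need a rule of interpretation to know whether a drug may be given.

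A reader might infer more than the documents support, in three ways.

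- *That fluvoxamine users can enter the trial, or that the SSRI permission undoes the inhibitor list generally.* Exclusion 10 closes the first, and only fluvoxamine is caught by the second.
- *That fluoxetine is wrongly left off the list.* The documents do not mention fluoxetine. The link to norfluoxetine as its metabolite is general pharmacology, and on the text as written an unlisted SSRI is allowed on study. The sponsor may have meant to ban fluoxetine or to allow it. That supports a question, not a finding.
- *That fluvoxamine would raise NLX-112 exposure by a known amount.* Section 6.1.3 reports a mean 2.5-fold increase (individual range 1.49 to 3.89) with ketoconazole. It gives no figure for fluvoxamine or fluoxetine, and the ketoconazole result cannot be carried over to them.

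**Conclusion.** The point holds as a low-severity contradiction. Of the 25 listed inhibitors, one, fluvoxamine, is both prohibited and allowed, and only for use that begins after Day 1. The conclusion rests on a literal reading of Section 9.6.2 and on fluvoxamine being an SSRI. The documents give no number of likely users, so no frequency can be attached to it. The sample size, endpoints and analysis model are unaffected. The norfluoxetine entry is unclear, but it is a matter for a query.

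**What to change.** Change the closing sentence of Section 9.6.2 to: *SSRIs are allowed, except those on the CYP3A4 inhibitor list above (fluvoxamine)*. The cost is one clause in the next amendment. The downside is that a patient who needs an SSRI during the study must use a different one.

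As a separate query, ask the sponsor whether norfluoxetine is meant to prohibit fluoxetine. If so, list fluoxetine and add it to the exception; this creates a named ban both at entry and on study, so it should be the sponsor's decision. If not, delete the entry.

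SAP Section 4.3 describes randomization in the past tense, so an amendment may come too late for patients already enrolled. In that case, use the concomitant-medication data, which the SAP tabulates to ATC level 5, to identify any fluvoxamine use and classify it by one rule before database lock. Correct the wording before it is reused in a later protocol.
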